46 end of the procedure the mucosal opening is closed with clips. In our centre we have
47 now treated more than 10 patients successfully with POEM and we were able to confirm
48 the positive findings in symptom improvement and lower oesophageal sphincter
49 pressure reduction reported by the German and Japanese pioneers of the technique.^{8,9}

50 **2 HYPOTHESIS**

51 We hypothesize that POEM has a higher long-term efficacy than PD in treatment of
52 therapy-naive patients with idiopathic achalasia.

53

54 **3 AIM**

55 To compare the efficacy of POEM to the efficacy of PD as the initial treatment of
56 symptomatic idiopathic achalasia.

57

58 **4 STUDY DESIGN**

59 This is a multi-centre randomised clinical trial in which a new treatment (POEM) will be
60 compared to the gold standard (PD). The primary endpoint will be measured at two
61 years after treatment and follow up will be extended up to five years.

62

63 **5 PRIMARY OUTCOME**

- 64 • Treatment success, defined as:
- 65 ○ An Eckardt score of 3 or less
 - 66 ○ The absence of the need for endoscopic or surgical retreatment in the
67 period between the first treatment session (first and optional second
68 dilation within first 3 months) and the endpoint
 - 69 ○ The absence of severe complications associated with treatment.

70

71 **6 SECONDARY OUTCOMES**

- 72 • Quality of life and achalasia-specific quality of life
- 73 • Stasis in the oesophagus, measured with a timed barium oesophagogram
- 74 • Presence of reflux symptoms, reflux oesophagitis and excessive oesophageal
75 acid exposure
- 76 • Lower oesophageal sphincter pressure and integrative relaxation pressure
77 (IRP4), as measured with high-resolution manometry
- 78 • Complications of the treatment, defined as any unwanted events that arise
79 following treatment and/or that are secondary to the treatment. Complications are
80 classified as “severe” when these result in admission > 24 hours or prolongation
81 of an already planned admission of >24 hours, admission to a medium or

82 intensive care unit, additional endoscopic procedures, or blood transfusion or
83 death. Other complications are classified as “mild”.

- 84 • The need for endoscopic or surgical retreatment after the initial treatment session

85

86 **7 POPULATION**

87 **7.1** *Subjects*

88 Adult patients with symptomatic idiopathic achalasia that have not undergone
89 endoscopic or surgical treatment for achalasia before.

90

91 **7.2** *Inclusion criteria:*

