- 92 • Presence of achalasia, as shown on oesophageal manometry
- 93 • Eckardt score > 3
- 94 • Age between 18-80 years
- 95 • Signed written informed consent
- 96 • ASA class I or II

97

98 **7.3** *Exclusion criteria*

- 99 • Previous endoscopic or surgical treatment for achalasia, except botulinum toxin
100 injections
- 101 • Previous surgery of the stomach or oesophagus
- 102 • Known coagulopathy
- 103 • Presence of liver cirrhosis and/or oesophageal varices
- 104 • Presence of eosinophilic oesophagitis
- 105 • Presence of Barrett’s oesophagus
- 106 • Pregnancy at time of treatment
- 107 • Presence of a stricture of the oesophagus
- 108 • Presence of malignant or premalignant oesophageal lesions
- 109 • Presence of an extensive, tortuous dilated oesophageal body (S-shape)
- 110 • Presence of a diverticula in the distal oesophagus

111

112

113 **8 METHODS**

114 **8.1** *Study protocol*

115 **Study enrolment and randomisation**

116 In the AMC, patients will be approached that visit the outpatient clinic of the Motility
117 centre of the Gastroenterology department. Patients should be diagnosed with achalasia
118 by manometry using the predefined manometric criteria and have not undergo surgical
119 or endoscopic treatment for achalasia before. Eligible patients will be given a verbal
120 explanation of the study. Each patient will receive a patient information brochure about
121 the study and an informed consent form for participation. Patients will be given sufficient
122 time to read the information and ask questions. Before any study procedures or
123 randomisation are initiated the patient must sign the informed consent form.

124

125 There is no time frame for the randomisation. When participants are recruited for the
126 study the time to consider participation in the study is unlimited. Before randomisation
127 the patient must have signed the informed consent form. Randomisation will be done
128 using a web-based program and is stratified for each centre, so that the number of
129 patients treated with POEM or pneumatic dilation is similar for each centre. The
130 randomisation for the two treatments will be 1:1.

131

132 **Baseline**

[figure not shown]
133 At baseline, patients will undergo oesophageal manometry, timed barium
134 oesophagography and upper endoscopy. A venous blood withdrawal is performed to
135 screen for abnormalities in blood count, chemistry lab and clotting. If any of these tests

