136 have been performed within the last 6 months and of high quality (at the discretion of the
137 investigator) it is not required to repeat this. Questionnaires regarding symptoms and
138 quality of life (see 8.4) are filled in by the patients.

139

140 **General follow up**

141 Patients that are randomised to endoscopic balloon dilation will be asked to fill in an
142 Eckardt score three weeks after the dilation. If this score is still more than 3, they will be
143 scheduled to undergo a second pneumatic dilation, but now using a 35 mm balloon
144 (figure 1). Manometry is performed if the Eckardt score is 3 or less. If the manometry

145 shows an IRP of more than 10, patients will also undergo a second pneumatic dilation
 146 (with a 35 mm balloon).
 147 Manometry and timed barium oesophagography are performed and questionnaires are
 148 filled in all patients 3 months after treatment and at 1, 2 and 5 years after treatment.
 149 Twenty-four hour pH-impedance monitoring is performed one year after treatment to
 150 evaluate oesophageal acid exposure. Upper endoscopy is performed at 1, 2 and 5 years
 151 after treatment.
 152
 153
 154

155
 156 *Figure 1 Treatment algorithm used in this study*
 157

158
 159
 160
 161
 162
 163

	Baseline	3 weeks*	3 months	1 year	2 years	5 years
Blood count, chemistry, clotting	X					
Questionnaires	X	Eckardt*	X	X	X	X
Timed barium oesophagography	X		X	X	X	X
Manometry	X	If Eckardt >3*	X	X	X	X
Upper endoscopy	X			X	X	X
pH-impedance monitoring				X		

164

165

Table 1 Schedule of baseline and follow-up examinations; * only for patients randomised to balloon dilation

166

167

168 **8.2 Pneumodilation (PD)**

169 In this study pneumodilation will only be performed by experienced endoscopists, that
170 have performed over 20 pneumodilation procedures. Patients are asked to use clear
171 fluids only starting 24 hours before the procedure and nil per mouth starting 8 hours
172 before the procedure. Under fluoroscopic guidance a Rigiflex balloon (Boston Scientific)
173 is positioned at the esophagogastric junction and dilated at a pressure of 5 PSI, followed
174 by dilation with 8 PSI for one minute (Figure 2).^{8,10} The initial pneumatic dilation is
175 performed using a 30-mm balloon. Three weeks later the symptoms of patients are
176 evaluated using the Eckardt score. If the Eckardt score is still higher than 3, a
177 subsequent dilation with a 35-mm balloon is scheduled. If the Eckardt score is less than

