420 advisory capacity to monitor participant safety and evaluate the efficacy and the overall
421 conduct of the study. The DSMB will be informed about adverse events and serious
422 adverse events that occur during the study. The advice(s) of the DSMB, in case it
423 influences the set-up of the study, will be notified upon receipt by the sponsor to the
424 METC that approved the protocol. With this notification a statement will be included
425 indicating whether the advice will be followed.

426

427 **10 STATISTICAL ANALYSIS AND RANDOMISATION**

428 We aim to perform an intention to treat analysis. After testing for normality, pairwise
429 comparisons will be performed between the two treatment arms for all primary and
430 secondary outcomes. Categorical variables will be compared using the Chi-square test.
431 The success rates of the two treatment arms will be compared using log-rank tests on
432 Kaplan-Meier estimates.

433 Randomisation will be done using a web-based online available program and is stratified
434 for each participating centre.

435

436 **11 SAMPLE SIZE ANALYSIS**

437 Recently reported complication free success rate of a two step PD strategy is 68% at
438 two years.⁶ Long term outcome data of POEM is lacking but at three months a success
439 rate of 94% has been described.⁹ Assuming success rates of 70% for PD and 90% for
440 POEM after two years, we estimated that with 62 patients in each group, the study would
441 have 80% power to detect a significant difference in success rate between PD and

442 POEM with a two-sided alpha level of 0.05. To cope with an estimated 5% loss to follow-
443 up, we aim to enrol 130 patients.

444

445 **12 PRIVACY**

446 The data of the subjects are coded in order of participation. The code and the data are
447 stored in different locations. The code can only be seen by the investigators. Qualified
448 authorities can get insight in code and data, but only when accompanied by the
449 investigators. Data will be stored 20 years after closure of the trial.

450

451 **13 ETHICAL CONSIDERATION**

452 The protocol of this study will be submitted to the Medical Ethical Committee of the
453 Academic Medical Center and will not start before formal approval has been granted.
454 Participants will be given oral and written explanation about the study, before they give
455 written informed consent. Subjects are allowed to withdraw informed consent without
456 providing arguments.

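### Secondary outcomes only: Section 10 picks the test by a normality pre-test and names neither baseline nor centre as a covariate, which may cost precision and leaves the effect measure unfixed

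*Protocol*

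**What the plan says.** Section 10 gives the rule in a single sentence: "After testing for normality, pairwise" "comparisons will be performed between the two treatment arms for all primary and" secondary outcomes. It then adds "Categorical variables will be compared using the Chi-square test", and a log-rank test for the success rates. It names no covariate, adjusted model or repeated-measures model. Sections 8.1 and 10 both say that randomisation is stratified by centre; the analysis does not mention centre.

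The baseline data exist. Section 8.1 says "At baseline, patients will undergo oesophageal manometry, timed barium" swallow imaging and endoscopy, and that questionnaires on symptoms and "quality of life (see 8.4) are filled in by the patients". Manometry and barium imaging are then repeated and questionnaires "filled in all patients 3 months after treatment and at 1, 2 and 5 years after treatment". Table 1 agrees. Section 6 lists the outcomes these measurements serve, among them general and disease-specific quality of life, barium stasis, and "Lower oesophageal sphincter pressure and integrative relaxation pressure".

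Acid exposure differs: "Twenty-four hour pH-impedance monitoring is performed one year after treatment to" assess it, with no baseline recording.

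**The concern.** Two features of the rule are weak for continuous outcomes.

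First, a plain two-arm comparison makes no use of a baseline value that is already in the database. If that value predicts the follow-up value, the interval for the treatment difference is wider than it need be. The trial was sized on the binary primary outcome and states no power for secondary outcomes, so precision there is worth having.

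Second, a normality test lets the data choose the method. The same outcome could be reported as a difference in means at one visit and as a rank comparison at the next, so the quantity being estimated is not fixed before the data are seen.

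**Working it through.** **Which outcomes qualify.** Those with a baseline value and a natural continuous scale are the two SF-36 summary scores, the achalasia-DSQoL, lower oesophageal sphincter pressure and IRP4. Barium stasis qualifies only if it is analysed as a continuous measure: Section 8.5 describes films at three times but defines no such measure. That makes five measures, or six with barium, at four follow-up visits: 5 × 4 = 20 or 6 × 4 = 24 comparisons, each with its own choice of test.

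**The plan's own figure.** Section 11 assumes 70% against 90% success, 80% power and two-sided alpha 0.05. With pooled variance and no continuity correction, n = [1.960·√(2·0.8·0.2) + 0.842·√(0.7·0.3 + 0.9·0.1)]² / 0.2² = (1.109 + 0.461)² / 0.04 = 61.6, so 62 per arm. The stated figure reproduces (power at 62 is 80.3%). It concerns the primary endpoint and is used below only as the number per arm.

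**Gain from baseline adjustment.** Relative to comparing follow-up values alone, ANCOVA has variance 1 − r², where r is the within-arm correlation between baseline and follow-up. Interval width scales by √(1 − r²), and the unadjusted analysis would need 62/(1 − r²) per arm for equal precision. For scale, take the standardised difference that has 80% power unadjusted at 62 per arm: √(2/62) × (1.960 + 0.842) = 0.503. The last column covers the case where the protocol means change from baseline. With equal variances at the two times, a change score has relative variance 2(1 − r), which is 2/(1 + r) times that of ANCOVA. All values of r are assumptions.

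| r | Variance ratio, adjusted to unadjusted | Interval width ratio | Equivalent n per arm | Power at 0.503 | Change-score variance relative to ANCOVA |
|---|---|---|---|---|---|
| 0.1 | 0.99 | 0.995 | 62.6 | 80.4% | 1.82 |
| 0.3 | 0.91 | 0.954 | 68.1 | 83.6% | 1.54 |
| 0.5 | 0.75 | 0.866 | 82.7 | 89.9% | 1.33 |
| 0.6 | 0.64 | 0.800 | 96.9 | 93.8% | 1.25 |

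**The pre-test.** The protocol does not name the two candidate tests, so an assumed pair was simulated: Shapiro-Wilk at 5% in each arm, then a t-test if both arms passed and Mann-Whitney otherwise (62 per arm, no true difference, 5,000 runs per distribution). Type I error was 5.0% for normal data, 4.8% for lognormal and 4.5% for gamma. The Monte Carlo standard error is √(0.05 × 0.95/5000) = 0.3 percentage points, so there is no sign of inflation. With exactly normal data both arms passed in 89.5% of runs, so the method switched to ranks in 10.5%. Over 20 comparisons that is an expected 20 × 0.105 = 2.1 switches by chance alone.

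**The case against.** **The method may be in the SAP.** Covariates for secondary outcomes are commonly left there, and the SAP is not at hand. That would answer a complaint about missing detail. Here Section 10 states a method, and a SAP that adjusted for baseline would depart from it. If the SAP already does so, only the protocol sentence needs aligning.

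**The protocol does not say that baseline is ignored.** A reader might infer that follow-up values alone are to be compared. The text does not say whether follow-up values or changes are meant, and it does not name the tests. This limit stands. What can be said is that no covariate is named, and that ANCOVA is at least as precise as either form, apart from the few degrees of freedom it uses.

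**The gain may be small.** This also stands. Treatment acts directly on the sphincter being measured, baseline tests may be up to six months old, barium volume varies with tolerance, and patients who fail are retreated and stay in follow-up. Each could weaken r. Quoting 83 per arm, the r = 0.5 row, as the cost of the plan would present an assumption as a fact.

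**Stronger readings that fail.** A reader might infer that the pre-test inflates false positives; the simulation does not show it. A reader might infer that chance baseline imbalance biases the result; under randomisation the unadjusted comparison is unbiased and its interval already allows for such imbalance, so this is the precision point counted twice. A reader might extend the point to GerdQ and acid exposure. Section 6 words the reflux outcomes as presence or absence, which falls under the Chi-square rule, and acid exposure has no baseline value.

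**Conclusion.** The point holds as a near-free improvement to a stated rule, for continuous secondary outcomes with a baseline value. The planned comparison is valid; it is neither biased nor anti-conservative on the evidence here. Two costs remain: precision that may be lost, and an effect measure that can change by outcome and visit.

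The variance reduction is about 1% at r = 0.1, 9% at 0.3, 25% at 0.5 and 36% at 0.6. This rests on an assumed r, on 62 analysed per arm, and on comparing with follow-up values alone. Against change scores the gain would be larger when r is below 0.5 and smaller when it is above. The documents give no way to size the effect of adding centre. Baseline adjustment leaves the primary endpoint, the 62 per arm, the binary outcomes and acid exposure unchanged.

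**What to change.** In Section 10, replace the normality-test sentence, for continuous secondary outcomes with a baseline value, with wording such as:

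> Each continuous secondary outcome that has a baseline value will be analysed by ANCOVA of the follow-up value on treatment, baseline value and centre (or by a mixed model for repeated measures over the visits with the same terms). The adjusted difference between arms will be reported with its 95% confidence interval. Outcomes expected to be skewed will be analysed after a named transformation or by rank-based ANCOVA, as listed by outcome before the data are compared by arm. No preliminary test of normality will be used.

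State whether barium stasis is a continuous measure and, if so, which one. If acid exposure is analysed as a continuous measure, fix its method in advance too, with centre as the only covariate.

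The cost is wording in Section 10 and any matching SAP text, agreed before outcomes are compared by arm. Statistically it uses one degree of freedom for baseline, out of 124 − 2 = 122, plus one fewer than the number of centres. Data collection, visits and sample size do not change.

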APPENDIX A

Calculation of the Eckardt score

Each patient has to answer four questions that concern different symptoms. Per symptom they have to mark the degree of severity of the specific symptom. Each symptom is scored from 0-3 and the Eckardt score is the sum of symptom scores. The minimum score is 0 and the maximum score is 12. A high Eckardt score indicates severe complaints due to achalasia.

Score	0	1	2	3
Questions/Symptoms				
Dysphagia (difficulty or pain during swallowing)	No (0)	Occasionally (1)	Daily (2)	At each meal (3)
Regurgitation (food is coming back in to the mouth)	No (0)	Occasionally (1)	Daily (2)	At each meal (3)
Chest pain	No (0)	Occasionally (1)	Daily (2)	At each meal (3)
Weight loss	0 kg (0)	0-5 Kg (1)	5-10 kg (2)	> 10 kg (3)

584
585
586
587
588
589
590
591
592
593
594
595
596
597
598
599
600
601

602 **16 ADDENDUM**

603

604 **Treatment failure in the POEMA Trial**

605

606 **Description of treatment failure**

607 Study subjects are considered treatment failures in case the **Eckardt score is > 3**
608 **within the first 2 years of follow-up, retreatment is indicated or a treatment related**
609 **SAE occurred** after the initial treatment. This means that the study subjects did not
610 achieve the primary endpoint, 2 years after the initial treatment, due to recurrent
611 symptoms.

612

613 The vast majority of failed study subjects will need retreatment and the indication for
614 retreatment should be based on the symptoms of the subject (Eckardt > 3) in
615 combination with:

- 616 - Considerable LES pressure or IRP (> 10mmHg) on HRM.
- 617 - Significant stasis on timed barium esophagogram.
- 618 - Clinical judgement and expert opinion of the treating physician.

619

620 **Treatment of treatment failures** (*see algorithm below*)

621 POEM procedure

622 Study subjects failed on POEM will be retreated with pneumodilation. The first step is to
623 perform a pneumodilation with a 30 mm rigiflex balloon in a single session. The effect of
624 the pneumodilation should be evaluated by the Eckardt score. In case the Eckardt is >3
625 a new pneumodilation should be scheduled with one step larger balloon size. There is
626 no limit to the number of pneumodilations that can be performed after a failed POEM.

627

628

629 Pneumodilation with 30 and 35 mm balloon

630 Study subjects failed on the initial pneumodilations (30 and 35 mm rigiflex balloon) within
631 the first year of follow-up will be retreated with a pneumodilation using a 40 mm rigiflex
632 balloon. In case subjects fail more than 1 year after the initial pneumodilations they will
633 be retreated with a pneumodilation using a 35 mm and 40 mm rigiflex balloon.

[figure not shown]
634 This is in contrast with the previous versions of the protocol concerning treatment failure
635 that stated that these patients should be subsequently treated with a POEM procedure.
636 The reason to retreat the patients first with a third pneumodilation of 40 mm is that the
637 optimal pneumodilation protocol is used in this way. After the additional
638 pneumodilation(s) symptoms should be evaluated by the Eckardt score. In case the
639 Eckardt is >3 the patient can be scheduled for a POEM procedure.

640

641 **Follow-up of treatment failures**

642 In principal, study subjects that failed on the initial treatment (2x pneumodilation or
643 POEM) achieved the primary endpoint at that moment. For these patients page 49,
644 study termination, of the CRF should be filled in.

645 It is very important to continue to collect the data of the treatment failures because sub-
646 analyses of these data can be performed at the end of the study. Therefore, follow up
647 will be the same as the study protocol; follow-up should be scheduled with regard to the
648 date of the initial treatment.

649
650
651
652
653
654
655

Treatment failure algorithm

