250 The average follow-up after the procedure described in the different articles was 3-5
251 months. No serious complications were observed during this follow-up period.
252 Furthermore none of the patients developed recurrent symptoms and symptoms of
253 gastro-esophageal reflux or reflux esophagitis were minimal.

254

255 **8.3.2** *Risk of complications in POEM in the first treated patients of the AMC*

256 In the AMC the POEM procedure is performed in more than 10 patients. There
257 were no serious adverse events (SAEs) preoperative or postoperative.
258 Preoperative two adverse events occurred in different patients. In one patient a
259 minor bleeding occurred during the cutting of the circular muscle layer which was
260 easily controlled by endoscopic coagulation. To be certain that the patient didn't
261 develop a rebleed, the patient stayed longer at the recovery for close monitoring.
262 Another adverse event that occurred during the procedure was a
263 pneumoperitoneum due to small transmural dissections into the mediastinum.
264 The pneumoperitoneum caused a temporary elevation of intraperitoneal pressure
265 which was relieved with an 18G canula, placed in the abdominal wall during the
266 procedure. The adverse events didn't extend the hospital admission and
267 reintervention was not needed.

268 Postoperative complications didn't occur. At this moment the follow-up period of
269 the treated patients is 1-6 months. None of the treated patients developed
270 recurrent symptoms so far and also gastro-esophageal reflux symptoms aren't
271 registered.

272

273 **8.4** *Questionnaires*

- 274 • Eckardt score, which is the sum of symptom scores for dysphagia, regurgitation,
275 chest pain and weight loss. Each symptom is scored from 0 to 3. The minimum
276 score is 0, the maximum 12. (see appendix A for explanation of the calculation of
277 the score)
- 278 • Medical Outcomes Study 36-Item Short-Form Health Survey [SF-36], The SF-36
279 mental and physical summary scores (which range from 0 to 100, with higher
280 scores indicating better well-being) measure general aspects of health quality of
281 life (12).

- 282 • The validated Achalasia Disease-Specific Quality-of-Life questionnaire
283 (achalasia-DSQoL).¹³
- 284 • The Gastroesophageal Reflux Disease Questionnaire (GerdQ) is a self-
285 assessment questionnaire that can be used for the diagnosis and follow-up of
286 gastroesophageal reflux disease, and measures both symptoms and impact of

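### The weight-loss item of the Eckardt score puts a loss of exactly 5 kg in two bands and names no reference weight or period, so some patients can total 3 or 4 at the cut that defines eligibility, success and failure

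*Protocol*

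**What the plan says.** Appendix A of the protocol defines how the score is built: "Each symptom is scored from 0-3 and the Eckardt score is the sum of symptom scores". The items are dysphagia, regurgitation, chest pain and weight loss. The weight-loss row reads "Weight loss 0 kg (0) 0-5 Kg (1) 5-10 kg (2) > 10 kg (3"). Section 8.4 names the same four items and sends the reader to Appendix A for the calculation. Neither place gives a starting weight, a date or a recall period for the loss.

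The boundary between 3 and 4 is then used in four places:

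- Section 7.2, eligibility: "Eckardt score > 3".
- Section 5, first component of treatment success: "An Eckardt score of 3 or less".
- Section 8.1, dilation arm only: patients complete an "Eckardt score three weeks after the dilation. If this score is still more than 3, they will be" booked for a second dilation.
- Addendum, treatment failure: the "Eckardt score is > 3" at any time in the first two years, or another failure criterion is met.

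Under section 8.1 and Table 1, the questionnaires are completed at baseline, 3 months, and 1, 2 and 5 years. There is an additional Eckardt score at 3 weeks for patients randomised to dilation.

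**The concern.** A scoring rule that feeds a dichotomous primary endpoint should give one score for one clinical state. This one does not, in two respects.

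First, the 1-point and 2-point bands share the value 5 kg. Two patients with the same loss and the same other symptoms can tick different cells and both be following the form. If their other items sum to 2, one is a success and the other a failure.

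Second, the form does not say what the loss is relative to. At baseline this matters less, because the illness itself supplies a natural starting point. At follow-up it decides whether weight lost before treatment and not regained still earns points. If some patients read the item that way, their follow-up score partly describes their state before treatment. The addendum counts a score above 3 at any point in the first two years as failure, so this can matter at each visit in that period and not only at two years.

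Neither problem can be repaired in the analysis. The patient marks a category, and once only the category is recorded, the kilograms and the reference weight behind it are lost.

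**Working it through.** **The plan's own figure.** Section 11 assumes 70% success with dilation and 90% with POEM, a two-sided alpha of 0.05 and 80% power, and states 62 per group. With the pooled-variance formula and no continuity correction:

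n = [1.960 × √(2 × 0.80 × 0.20) + 0.842 × √(0.70 × 0.30 + 0.90 × 0.10)]² / 0.20² = (1.109 + 0.461)² / 0.04 ≈ 61.6, so 62 per group.

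Power at 62 per group is 0.803. The figure reproduces, and nothing below changes it.

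**Boundary values of the weight-loss bands (Appendix A).**

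- 0 kg: has its own 0-point cell and is also the lower end of the 1-point band. The dedicated cell resolves it.
- 5 kg: upper end of the 1-point band and lower end of the 2-point band. Nothing resolves it.
- 10 kg: only in the 2-point band, because the top band starts above 10.

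The one real overlap is at 5 kg.

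**When the overlap changes a decision.** Let S be the sum of the other three items, each 0 to 3. A 5 kg loss gives a total of S + 1 or S + 2. The two totals lie on opposite sides of the cut when S + 1 ≤ 3 and S + 2 > 3, that is, when S = 2. The totals are then 3 and 4.

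The other three items have 4 × 4 × 4 = 64 combinations. Those summing to 2 are one item at 2 with the others at 0 (3 ways), or two items at 1 with the third at 0 (3 ways). That makes 6 of 64. This counts possible combinations and does not say how often patients have them.

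**What 3 versus 4 means.**

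- Section 7.2: 3 is ineligible, 4 is eligible.
- Section 5: 3 meets the symptom component of success, 4 does not.
- Addendum: 3 is not a failure on symptoms, 4 is.
- Section 8.1 at 3 weeks: 4 leads to a second dilation; 3 leads to manometry, and then to a second dilation if the IRP is above 10. The ambiguity therefore changes whether a second dilation occurs only when the IRP is 10 or less.

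**The missing reference.** Take a patient who lost more than 10 kg before treatment, has not regained it, has lost nothing since, and reports one other symptom occasionally (S = 1). Measured from weight before the illness, the total is 1 + 3 = 4, a failure. Measured from weight at treatment, it is 1 + 0 = 1, within the success range. Appendix A permits both readings. This shows what the wording allows, not how patients in the trial will read it.

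**The case against.** The strongest reply is that the overlap is tiny and the rest is conjecture. Much of that stands.

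- The overlap affects only a loss of exactly 5 kg combined with a sum of exactly 2 on the other items.
- A reader might infer that the result depends on who codes the form. The protocol does not support this: Appendix A has the patient mark a category, and no coder is described. The ambiguity lies in what the patient ticks. Nor does the form ask for a figure in kilograms, so one cannot assume that 5 kg will be a common answer.
- A reader might infer that the item measures loss before treatment and so turns true successes into failures in both arms. That is one possible reading. Appendix A presents a high score as a sign of current complaints, and a follow-up symptom score is naturally read as present state. The addendum refers to a case report form that is not shown and may carry an instruction.
- A reader might put a number on lost power. Any such number needs a misclassification rate, and the document gives none. It would also treat the 70% and 90% in section 11 as free of scoring error, which nothing establishes.
- A reader might infer that the ambiguity pushes dilation patients into a second dilation. The manometry route in section 8.1 limits this, and section 8.2 does not count that dilation as failure.

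What does not fall away is the text itself. One value belongs to two scores and the reference is unstated, in the instrument that defines the primary endpoint. An unseen form might settle the reference, but the protocol points to Appendix A for the calculation, and Appendix A does not settle it.

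**Conclusion.** The point holds as a defect in the definition of the score. A loss of exactly 5 kg can be scored 1 or 2. With the other items summing to 2, that places the same patient on either side of the cut for eligibility, success and failure. The reference for the loss is not stated, so follow-up scores may partly carry earlier loss if patients read the item that way.

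The size is small for the overlap and unknown for the missing reference. The document gives no frequency for either, so no effect on power, on the treatment difference or on its direction can be claimed. The sample size of 62 per group reproduces and stands. The conclusion assumes that the questionnaire patients receive carries the same bands as Appendix A and no further instruction. If the form already fixes the reference, only the 5 kg overlap and the silence of the protocol remain.

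**What to change.** In Appendix A and on the questionnaire, make the bands disjoint, for example: none; more than 0 and under 5 kg; 5 to 10 kg; over 10 kg. Which side the boundary value falls on matters less than that it falls on one side only.

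Print one reference period for the weight-loss item on the form, the same in both arms, at all centres and at every follow-up visit. It should not be tied to the previous assessment. Only the dilation arm has a 3-week Eckardt score, so at 3 months one arm would be scored from 3 weeks and the other from an earlier point. The windows would also stretch from weeks to the three years between the 2-year and 5-year visits, under the same kilogram limits.

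The sponsor should choose the reference and reconcile it with every passage that uses the Eckardt cut for a treatment decision. Three of those passages already disagree on 3-week manometry: section 8.1 sends scores of 3 and below to manometry, section 8.2 only scores below 3, and Table 1 lists manometry for scores above 3. They must be reconciled as well.

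The change to the item costs a line or two in Appendix A and on the questionnaire, with no extra visits or data. It must be made before the forms are completed, because ticked categories cannot be re-scored.
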